9.8.6. SIDIAP (ES)

QC processes will be implemented at each phase of the data flow cycle. QC checks will be performed at the extraction and uploading steps. To assess data completeness, the presence of elements will be described by geographical area, registering physician, time and the distribution of values. The accuracy of the data will be assessed by validity checks on outliers, out of range values, formatting errors and logical date incompatibilities.

Completeness and accuracy measures will be used to inform decisions on the required transformations to improve data quality (eg, harmonisation, normalisation, and clean-up) and the fitness for purpose of the data for use in this study.

9.8.7. CPRD (UK)

The Drug Safety Research Unit (DSRU) will have information security policies in place to preserve the confidentiality, integrity and availability of the organisation's systems and data. These will include ensuring that the premises provide suitable physical and environmental security, all equipment will be secure and protected against malicious software, the network will be accessed only by authorised staff, telecommunication lines to the premises will be protected from interception by being routed overhead or underground, and personnel will receive training on security awareness. The study will be conducted in compliance with the International Society for Pharmacoepidemiology *Guidelines for Good Pharmacoepidemiology Practices (GPP)*⁴⁸ and the *ENCePP Code of Conduct*.¹⁴ Data quality is a high priority at the DSRU and will be assured through a number of methods based on staff training, validated systems, error prevention, data monitoring, data cleaning, and documentation, including the following:

- staff training on data processing standard operating procedures;
- data management plan for every research study outlining the legal basis for data collection, data flows, data access rights, data retention periods, etc.;
- routine data cleaning to screen for errors, missing values, and extreme values and diagnose their cause;
- system process logs to document staff access, etc.

9.9. Limitations of the research methods

This study is subject to limitations related to both the study design and to the use of secondary health care data.

A data-related limitation of this study is the reliance on the accuracy of codes and algorithms to identify outcomes. Some outcomes and their dates of occurrence will be validated, but the extent of validation may be limited because of only partial access to medical records. It is

possible that some AESIs may be due to immunisation errors occurring during the administration of the bivalent BA.1 or bivalent BA.4-5 vaccines. This information is not regularly collected and it will not be possible to take these events into account with the current protocol. Exposure identification may be based on pharmacy dispensing records, general practice records, immunisation registers, medical records, or other secondary data sources. How specific COVID-19 vaccine products and dates of vaccination in these data sources will be identified is described in [Section 9.3.1](#). It is possible that vaccination of individuals outside the health care system will not be recorded in secondary EHR databases, thereby leading to potential bias because of exposure misclassification. Additionally, while every effort will be made to capture data on all variables, some data may not be identified or recorded in the data sources.

A study design-related limitation of both the cohort and SCRI designs is that any uncertainty regarding risk periods will lead to misclassification and underestimation of the risk. The estimation of cumulative incidence curves with a time zero starting on the date of the exposure assignment and eligibility assessment will minimise the impact of unknown risk periods, because there is an unvaccinated comparator and evaluation is done over the whole available follow-up.

A limitation of the cohort design is the potential for residual or unmeasured confounding, as it is unlikely that the data sources will have information on all potential confounders. To address potential confounding, the SCRI, which automatically adjusts for time-invariant confounders, will be used as a secondary approach. However, the SCRI is not well-suited to study outcomes with gradual onset, long latency, or risk periods that are not well known. It also may be subject to bias for outcomes that affect the probability of exposure. The SCRI design will be used as a secondary approach to the cohort design for prespecified AESI with defined risk intervals. Of note, several safety and efficacy studies comparing vaccination vs. no vaccination using a matched cohort design with matching variables similar to those that will be used in this study have been reported, and good adjustment for confounding was obtained.²¹⁻²⁵

The matching procedure in the cohort analysis produces a study population (ie, a set of matched pairs) with a distribution of matching variables representative of the exposed by matching unexposed individuals to exposed individuals based on a prespecified set of baseline variables. Therefore, the cohort analysis estimates the average causal effect in the vaccinated (ie, in a population that has the distribution of matching variables of the vaccinated). If further adjustment via inverse probability weighting is applied, because the weights are estimated and applied to the matched population, the estimated effect will still be the causal effect in a population that has the distribution of matching variables of the vaccinated. The average causal effect in the vaccinated and the average causal effect in the whole population (vaccinated and unvaccinated) should differ only (apart from random variation) if effect modification by any baseline variable exists. This will have to be considered when comparing effect estimates with those from other studies.

Finally, the extrapolation of the study results to other European countries that not participated in the current analyses and non-European countries should be done cautiously if relevant differences in the populations exist.

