9.1.1.3. Matching process

As in prior applications of observational studies of the Pfizer-BioNTech COVID-19 using an unexposed comparator,²¹⁻²⁴ the cohort study will match exposed to unexposed individuals using a 1:1 ratio. Matching will be done with replacement, as follows.

- On the day an exposed individual receives a bivalent vaccine dose, individuals will be matched to unexposed individuals who, on that same day, have exactly the same values for the matching variables, provided that both members of the pair meet the eligibility criteria that day. If more than one unexposed individual is found to match a bivalent vaccinated individual, one will be selected at random.
- Exposed individuals will be allowed to have served as unexposed controls in prior matches, and unvaccinated individuals will be allowed to serve as controls more than once (during different time periods).

Individuals will be matched on the following variables, that have been shown to control for confounding well in prior studies:^{21,22}

- Age – 2-year age groups (consecutive years);
- Sex (male, female) – exact matching;
- Place of residence – exact matching, at the level of clinical practice, neighbourhood, or proxy as available (specific for data source);
- History of COVID-19 vaccination, containing the following categories – exact matching:
 - Never vaccinated;
 - Vaccinated with a total of i doses (where i can range from 1 to the maximum number of plausible doses at the time the matching is performed) with the last dose received in calendar month j (where j can range from the first month to the last month of the study period);
- Brand of last COVID-19 vaccine received;
- History of hospitalisation for COVID-19;
- Pregnancy status yes, no (exact matching):
 - Among pregnant women, matching will take a ‘greedy matching’ approach, in which a matched individual will be sought first by last menstrual period (LMP) within 7 days of each other; if no matches are found, the matching period will be extended to 30 days;
- Immunocompromised (yes/no) – exact matching;
- Number of pre-existing conditions considered by the Centers for Disease Control and Prevention (CDC) as risk criteria (0, 1, >1);²²
- Socioeconomic status/education level (as available, exact matching);
- This selection of matching variables is based on prior observational studies.^{22,24,25} The selection of variables will be tailored based on the availability of variables in each data source.

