9.2. Setting

9.2.1. Inclusion criteria

9.2.1.1. Cohort design

- Individuals must meet all the following criteria to be eligible for inclusion in the cohort study:
 - have a minimum of 12 months (or from birth if enrolled in the data source at birth) of continuous enrollment in the data source at time zero;
 - have complete information on the matching variables;
 - be in the population targeted by recommendations for vaccination with the bivalent BA.1 or BA.4-5 COVID-19 vaccines, either as a booster, ie, an additional dose several months or longer after the two or three-dose primary vaccine series, as per national or regional recommendations, or as primovaccination, ie, as the first ever COVID-19 vaccine received:
 - if an individual has not received any COVID-19 primovaccination, they will meet this criterion;
 - if an individual has received primovaccination, they will meet the above criterion if they:
 - meet the age threshold or other criteria for additional COVID-19 vaccine doses after primovaccination;
 - do not have any comorbidities or other characteristics for which a short interval between doses is recommended by local vaccination policies and have had prior COVID-19 vaccination at least 11 months before baseline;
 - have comorbidities or other characteristics for which a short interval between doses is recommended by local vaccination policies and have had prior COVID-19 vaccination at least 5 months before baseline.

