 - **EpiChron:** The EpiChron Cohort Study links socio-demographic and clinical anonymised information for all the inhabitants of Aragon region, built from the BIGAN platform. The Aragon BIGAN platform integrates a technical infrastructure and a data lake

gathering individual data from the regional health service information systems, including primary care, specialised care, hospitalisations, ER episodes, drug prescriptions, image diagnosis, laboratory tests, diagnostics, vaccination, medical history and demographics from the users of the public health system of Aragon, about 2 million individuals with historic data, and an active population of 1.3 million individuals.

- SIDIAP:** The Information System for the Improvement of Research in Primary Care (Sistema d’Informació per al Desenvolupament de la Investigació en Atenció Primària’ [SIDIAP]) SIDIAP includes data from 328 primary care centres managed by the Catalan Health Institute in Catalonia, Spain. The database contains pseudo-anonymised records for >8 million people since 2006, with 5.8 million people active in June 2021 (75% of the Catalan population). SIDIAP is representative of the general population living in Catalonia in terms of age, sex and geographic distribution ³⁴. SIDIAP includes data on the clinical and referral events registered by primary health care professionals and administrative staff in EHRs, demographic information, community pharmacy invoicing data, specialist referrals, and primary care laboratory test results. SIDIAP data can be linked to other data sources and registers at the local and national level.
- UK: Clinical Practice Research Datalink (CPRD)**

 - CPRD includes data from EHRs of general practitioners in the UK who act as gatekeepers for health care and maintains individuals’ life-long EHRs. Secondary care teams also provide information to general practitioners about their patients, including key diagnoses and procedures. The data recorded in the CPRD include demographic information, prescription details, clinical events, preventive care, specialist referrals, hospital admissions, and major outcomes, including death. Currently, CPRD Aurum contains data for approximately 13.3 million individuals [Current acceptable individuals (ie, registered at practices currently contributing data, excluding transferred out and deceased individuals)].

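### Section 9.9 claims the average effect in the vaccinated without condition, but exact matching with no general fallback yields the effect in matched vaccinees only

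*Protocol*

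**What the plan says.** Section 9.9 describes the matched pairs as having the exposed group's distribution of matching variables. It then concludes: "Therefore, the cohort analysis estimates the average causal effect in the vaccinated (ie, in a population that has the distribution of matching variables of the" [exposed group]). It adds that any further weighting is estimated and applied in the matched population, so that the target stays the same.

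Section 9.1.1.3 sets the rule: "the cohort study will match exposed to unexposed individuals using a 1:1 ratio. Matching will be done with replacement", and on the vaccination day "individuals will be matched to unexposed individuals who, on that same day, have exactly the same values for the matching variables". Ten variables are listed: two-year age group, sex, residence, vaccination history (number of doses and calendar month of the last one), brand of last vaccine, COVID-19 hospitalisation, pregnancy, immunocompromise, number of CDC risk conditions, and socioeconomic status. Residence reads "Place of residence – exact matching, at the level of clinical practice, neighbourhood, or proxy as available (specific for data source").

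Only one step is written for a failed match. Among pregnant women, the last-menstrual-period window widens from 7 to 30 days. The tailoring clause at the end of the section depends on which variables a source holds, not on whether a match was found. Section 9.2.1.1 also requires people to "have complete information on the matching variables".

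**The concern.** A matched set has the covariate distribution of the vaccinated only if almost every eligible vaccinee enters it, or if those who fail to match resemble the rest. Exact matching on ten variables makes failure most likely in sparse cells, such as immunocompromised people or those with a previous COVID-19 hospitalisation. These are characteristics on which a vaccine's safety profile might differ.

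Section 9.9 already warns that the effect in the vaccinated can differ from the effect in the whole population when there is effect modification. The same reasoning applies between matched and all vaccinees, but the section does not apply it there. If many vaccinees are unmatched, a reassuring cohort result would be reported for a wider population than the one that produced it. Section 9.3.5 plans an immunocompromised subgroup, so the gap bears on a stated analysis.

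**Working it through.** **1. The plan's only study-size figures.** The protocol gives no match rate. Table 3 in section 9.5 follows from the Wald interval for a log risk ratio, SE = √(1/a − 1/n + 1/b − 1/n). For n = 1,000,000 per group, risk 1 per 50,000 and risk ratio 2, the expected events are a = 40 and b = 20. SE = √(1/40 + 1/20 − 2/1,000,000) = 0.274, and 2 × exp(±1.96 × 0.274) gives 1.17 to 3.42, as printed. Of the 27 rows, 22 were checked and all reproduce; the largest gap is 3960.02 against 3960.57. Table 3 is therefore right, provided its group size is read as the number of matched pairs. If 1,000,000 vaccinees yield 500,000 pairs at the same risks, a = 20 and b = 10, and the interval is 0.94 to 4.27 (re-use of controls ignored).

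**2. When the 9.9 statement is true.** Let π be the share of eligible vaccinees matched, and let D_m and D_u be the risk differences in matched and unmatched vaccinees. The effect in the vaccinated is π·D_m + (1 − π)·D_u, while the cohort estimates D_m. The gap is (1 − π)(D_u − D_m). It vanishes only if π = 1 or D_u = D_m. Weights fitted among matched people contain nothing on D_u and cannot close it.

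**3. How large 1 − π might be.** Section 9.4 says "SIDIAP includes data from 328 primary care centres managed by the Catalan Health Institute in Catalonia, Spain", with 5.8 million active people: 5,800,000 / 328 = 17,683 per centre. EpiChron's active population is 1.3 million, used here as a unit the size of a whole region. The matching rule was simulated: a vaccinee is matched if anyone in the same unit and exact stratum has not yet received a bivalent dose that day.

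Assumptions not in the protocol: 40 two-year age bands; 50% male; 0 to 4 prior doses at 15/5/25/45/10%; eight last-dose months with declining frequency; three brands at 60/30/10%; 2% previously hospitalised for COVID-19; 1 or 5 socioeconomic levels; 2% or 5% immunocompromised, all with at least one risk condition; bivalent uptake of 30% or 60% in the previously vaccinated. Interval eligibility and pregnancy were not modelled.

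| People in residence unit | All vaccinees matched | Immunocompromised matched |
|---|---|---|
| 2,000 | 4-22% | 0-3% |
| 8,000 | 15-52% | 1-8% |
| 17,683 (SIDIAP centre) | 27-69% | 1-16% |
| 100,000 | 64-91% | 7-52% |
| 1,300,000 | 94-99% | 46-92% |

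At the SIDIAP-centre size, 1 − π is 31-73%, so that share of any difference D_u − D_m separates the estimate from the stated target. At 1.3 million it is 1-6%.

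**4. Effect on composition.** The immunocompromised share of the matched set is p × (their match rate) / (overall match rate), where p is their share of vaccinees. With p = 5%, one socioeconomic level and 30% uptake:
- SIDIAP-centre size: 5% × 0.16 / 0.67 = 1.2%.
- 1.3 million: 5% × 0.92 / 0.99 = 4.6%.

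With five levels and 60% uptake, these become 5% × 0.03 / 0.27 = 0.6% and 5% × 0.67 / 0.94 = 3.6%. The share is below 5% each time, slightly or severely depending on the unit.

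**The case against.** The strongest reply is that this is one loose sentence. Section 9.9 itself calls the study population a set of matched pairs and separates that effect from the whole-population effect. Leaving some vaccinees unmatched changes whom the estimate describes but does not invalidate the matched contrast. That is right, and no bias within the pairs is alleged here. The sentence still names the wrong population without condition.

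Three stronger readings are tempting, and the protocol does not support them.

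- *Unmatched vaccinees have no path into any analysis.* Sections 9.1.2 and 9.2.1.2 admit vaccinees with an event to the SCRI without a matched comparator, and section 9.3.5 plans the immunocompromised subgroup there too. The SCRI is secondary, however. Table 1 leaves death, heart failure, arrhythmia, acute kidney injury and severe COVID-19, among others, to the cohort alone, and pregnancy outcomes to sub-cohorts.
- *Matching is at clinical-practice level.* That is one of three permitted levels, chosen by data source. Nothing says SIDIAP will match on centre.
- *The study nearly loses the immunocompromised.* This holds in the simulation only for small residence units and rests on assumed distributions.

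Matching with replacement and the use of later vaccinees as controls both raise match rates; the simulation allows for both. For people with incomplete matching variables, section 9.7.1.10 lists weighting of complete cases as an option, so that part of the loss may be addressed. The SAP is not at hand and may add a matching fallback or attrition tables, so the absence of such detail is not the finding. The finding is the unconditional claim in the protocol.

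**Conclusion.** The point holds as one about the target population. As sections 9.1.1.3 and 9.9 stand, the comparative cohort estimates the effect in vaccinees who found an exact match. That equals the effect in all eligible vaccinees only if nearly all are matched or if match failure is unrelated to effect modifiers. Neither condition is stated or secured.

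The size cannot be read from the protocol. The simulated range is wide, and the residence unit drives most of it. The immunocompromised were matched less often than vaccinees overall in every scenario; how much less depends on the unit and on the assumed prevalence, socioeconomic levels and uptake. A reader might infer that the cohort describes only healthier vaccinees, but that is a possibility to check in the data and not something the protocol shows.

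**What to change.** In section 9.9, say that the cohort estimates the average effect in matched vaccinees, and that this equals the effect in all eligible vaccinees only if nearly all are matched or if match failure is unrelated to effect modifiers. List unmatched vaccinees among the limitations.

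In section 9.7.1.2, require the matched fraction per data source and a comparison of matched with unmatched vaccinees by age, immunocompromise and prior COVID-19 hospitalisation. Both can be produced from the matching output, so the cost is wording and one table.

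Optionally, as a sensitivity analysis, add a second matching pass on a wider residence unit or weight pairs by the inverse probability of being matched. The second pass trades coverage for coarser residence control, which region in the propensity score can partly offset. Weighting cannot represent kinds of vaccinee who never match. Neither option is needed to correct the statement.

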9.10. Other aspects

Not applicable.

10. PROTECTION OF HUMAN SUBJECTS

This is a non-interventional study using secondary data collection and does not pose any risks for individuals. Each DAP will apply for an independent ethics committee approval according to local regulations.

Data protection and privacy regulations will be observed in collecting, transferring, processing, and storing data from study participants.

10.1. Participant information

This study will involve mainly data that will be in an anonymised structured format that will contain no participant personal information. In compliance with DAPs policies¹, in all cells with less than 5 counts for AESIs the actual number will be replaced by <5 to avoid potential identification of individuals.

All parties will comply with all applicable laws, including laws regarding the implementation of organisational and technical measures to ensure protection of participants' personal data. Such measures will include omitting participants' names or other directly identifiable data in any reports, publications, or other disclosures, except where required by applicable laws.

Participant personal data will be stored by the DAPs in encrypted electronic form and will be password protected to ensure that only authorised study staff can access them.

DAPs will implement appropriate technical and organisational measures to ensure that personal data can be recovered in the event of disaster. In the event of a potential personal data breach, DAPs shall be responsible for determining whether a personal data breach has in fact occurred and, if so, providing breach notifications as required by law.

To protect the rights and freedom of natural persons in terms of the processing of personal data, when study data are compiled for transfer to Pfizer and other authorised parties, any participant names will be removed and will be replaced by a single, specific, numerical code. All other identifiable data transferred to Pfizer or other authorised parties will be identified by this single, patient-specific code. In the case of data transfer, Pfizer will maintain high standards of confidentiality and protection of individuals' personal data consistent with the vendor contract and applicable privacy laws.

¹ The data sources concerned by this rule are : PHARMO, NHR, EpiChron, SIDIAP and CPRD.

